Feasibility Testing (Aim 1): We will demonstrate feasibility, acceptability, and validity of the SPEEKO for Elderspeak feedback app use by staff in the NH and identify needed modifications prior to testing in Aim 2. The PI worked with the Speeko Company (see resources and letter) to develop the elderspeak feedback app. App proof of concept has been

demonstrated in the lab setting. With a preliminarily trained natural language processing detection model, diminutive accuracy testing resulted in a sensitivity (true positive rate) of 87.7% and a specificity (true negative rate) of 99.9%. The app provides immediate feedback with potential to increase CHATO effects. Recordings are analyzed by a natural language processing app that provides immediate and private feedback and encouragement to individual staff. The app detects common elderspeak terms of endearment (diminutives), identified through reanalysis of the PI's archived NH recordings.⁵⁶ Detection algorithms were also developed using the recordings to establish proof of concept. App modifications were completed to enhance recording quality and transcription accuracy and to filter noise.

Further feasibility and detection model algorithm optimization will be tested at Garden Terrace of Overland Park, a NH dedicated to dementia care. A detailed protocol and user manual will be developed, and pilot tested. Feasibility will be tested with five CNA volunteers (n=5) who will each record a 2-hour care session. These staff will record their speech during a 2-hour work session to demonstrate use of the feedback app and complete a 10-item usability scale. Potential issues (e.g., background noise, Internet and bandwidth adequacy, acceptability to residents) will be assessed. App outputs will be compared to data from transcription and psycholinguistic coding, using our established protocols, to validate app reliability for diminutive detection. The CNAs will be interviewed about use of the app, providing additional data to improve the system for Aim 2 testing. If validated, app functions may be expanded to monitor additional aspects of elderspeak (i.e., "we" pronoun substitutions).

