Data Archiving. After each recording session, the Project Director will screen and edit recordings to delete any resident or other staff communication or other identifiers (names) so that the archived recording contains only the desired CNA participant's voice. Recordings and data will be archived in a dedicated research computer labeled with unique identifier codes. To reduce the Hawthorne effect, the initial 15 minutes of each recording session will be discarded. An estimated hour of recorded speech will be collected four times for each of

60 CNAs, providing approximately 240 hours of recordings for transcription, coding, analysis, and additional app algorithm training.

Psycholinguistic Coding. RAs will transcribe all recordings (for both groups) and will use brackets to code diminutives using our established operational definitions and protocols.^{10,43,45,56,78} To assure reliability, as used in our past studies, RAs will be trained on a practice sample until achieving 90% agreement for utterance segmentation and coding. A second trained coder will independently code 10% of the actual study transcripts. Additional training will be provided if agreement falls below 85%. Systematic Analysis of Language Transcripts (SALT)⁷⁹ will be used to tabulate frequencies for each code. Data will be entered in an electronic spreadsheet using unique identifier codes and stored on a secure computer. RAs will not have access to the key connecting codes with identifying information and will be blind to group assignment and assessment time points.

Acceptability and Cost Testing (Aim 3): CNAs testing the app will complete the System Usability Scale (SUS), a validated 10-item industry standard survey to rate (1) use of the microphone, recorder, and app; (2) acceptability and work compatibility; (3) feedback infographic; and (4) interest in self-monitoring. We hypothesize that staff who use the app will find it acceptable and beneficial for their practice. As in our prior studies, we will use process-based costing to determine average costs for using the SPEEKO for Elderspeak feedback app, comparing costs relative to any difference determined for reductions in diminutive use in the immediate and delayed feedback groups.^{80,81} Evaluation of acceptability and costs are key factors in consideration of ongoing plans for app dissemination in NHs and across other long-term services and support settings.

C. Sample size, statistical methods, and power calculation

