Aim 1: We will demonstrate feasibility, acceptability, and validity of the SPEEKO for Elderspeak feedback app with detection model algorithm optimization with a diminutive accuracy testing benchmark of 80% or higher. App outputs will be compared to data from transcription and psycholinguistic coding, using our established protocols, to validate app reliability for diminutive detection. Also, an analysis of a CNA-completed, 10-item usability scale (The System Usability Scale) with an acceptability benchmark of 50% or higher.

Aim 2: Linear Mixed Models (LMMs) or Generalized LMMs, depending on the distribution of each outcome, will be developed to determine the impact of group assignment (feedback or no feedback) on use of elderspeak diminutives. Baseline diminutive use, group (feedback vs. no feedback), recording session (pre- and post CHAT sessions 1, 2, and 3), and interaction between intervention and session will be fitted as fixed effects. To account for clustering, each NH will be fitted as a random effect. To account for correlation due to repeated measurements, an appropriate covariance pattern will be determined from data. CNA and resident sex and CNA knowledge gain will be tested as covariates. Aim 2 will estimate variability, effect sizes, and intracluster correlation for a future larger-scale study. Sample sizes of as few as 30 in each group, or 10 CNAs on average in each NH, will achieve 80% power to detect a difference between the group means of 0.74 to 0.76 standard deviations, assuming the intracluster correlation coefficient ranging from 0.001 to 0.01 and coefficient of covariation among cluster sizes of 0.25. A two-tailed t-test was used with a significant level of 0.05 and the degrees of freedom based on the number of subjects.

Aim 3: We will use process-based costing to determine average costs for using the SPEEKO for Elderspeak feedback app, comparing costs relative to any difference determined for reductions in diminutive use in the immediate and delayed feedback groups.^{80,81}

D. Subject Criteria (See Vulnerable Populations appendix, if applicable):

1. Inclusion criteria: We will recruit CNAs who are age 18 or older, permanent employees, and fluent in English to participate. Descriptive information (age, sex, race, ethnicity, role, experience) will be used to identify CNA covariate factors predicting communication

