1. The PI and other research team members as delegated will conduct an audit at least annually including review of a random sample of at least 3 CNAs who participate in CHATO training and participate in audio recording for compliance with study protocols including informed consent documents, data storage documentation and deidentification of data. The PI will conduct an annual review of research team member compliance with IRB required training and certification. The PI or delegate will train and supervise research team members in recruitment and consenting procedures, data collection, provision of intervention, and data analysis and coding on a quarterly basis. Specific procedures to assure fidelity and compliance with the protocol are included in the research plan.
2. The **SMC** will initially review and approve the written study protocol, data collection and storage protocols, intervention materials, informed consent procedures, and this plan for data and safety monitoring. Any outside agreements with vendors and subcontractors will be reviewed. The SMC will also review the general reporting guidelines based on the study procedures approved by IRB. Reporting rules will be established taking into consideration the population under study and anticipated

adverse outcomes (reflected in the human subjects consent documents). Prior to study implementation, the SMC will identify pre-specified stopping rules that will be employed if significant benefits or risks have developed, if trial management issues prevent successful completion, or if compelling ethical concerns arise.

V. Data Analysis and Reporting

A. Statistical and Data Analysis:

1. **AIM 1.** Demonstrate feasibility, acceptability, and validity of the SPEEKO for Elderspeak feedback app use by staff in the NH. Five certified nursing assistants (CNAs) will use the app during NH care and provide feedback about any needed modifications. **Analysis:** A 10-item usability scale. Success will be determined by a cumulative score of 80% or more.
2. **AIM 2.** Test preliminary effects of an innovative self-monitoring feedback app on staff elderspeak use and compare accuracy to psycholinguistic analyses of audio-recorded staff communication. **Statistical Analysis:** Linear Mixed Models (LMMs) or Generalized LMMs, depending on the distribution of each outcome, will be developed to determine the impact of group assignment (feedback or no feedback) on use of elderspeak diminutives.

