3. **AIM 3.** Evaluate app acceptability and costs. **Analysis:** Process-based costing to determine average costs for using the SPEEKO for Elderspeak feedback app, comparing costs relative to any difference determined for reductions in diminutive use in the immediate and delayed feedback groups.

B. Outcome:

1. **AIM 1 Expected Outcome:** The app will be readily used and acceptable to CNAs. Diminutive counts determined by the app will be correlated with psycholinguistic analysis, validating accuracy.
2. **AIM 2 Expected Outcome:** Staff who receive immediate app feedback (N= 30 in three NHs) will have greater elderspeak reduction after completing CHATO training compared to delayed feedback controls (N= 30 in three NHs).
3. **AIM 3 Expected Outcome:** Staff who use the app will find it acceptable and beneficial for their practice. Process-based costing will be used to determine costs for app use in NHs and other long-term service and support settings. Costs will be compared in relation to each group's outcomes.

C. Study results to participants: Audio recording feedback via the app will be provided either immediately after recording (treatment group) or at the end of the study (control group). Nursing homes will receive CHATO participation rate feedback.

D. Publication Plan: The PI will develop an appropriate plan for publication of research results based on the study aims and results.

VI. Bibliography / References / Literature Cited

1. Department of Health and Human Services. *National plan to address Alzheimer's disease: 2015 Update*. 2015.
2. Alzheimer's Association (2017). Alzheimer's Disease Facts and Figures.

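### Aim 1 has two pass marks for the same usability scale, 50% in II.C and 80% in V.A.1, and the conflict should not be settled at 50%, which five indifferent CNAs would meet half the time or more

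*Combined protocol and SAP*

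**What the plan says.** Aim 1 is to demonstrate feasibility, acceptability and validity of the app before the cluster trial. Its hypothesis (I.A, repeated in V.B.1) is: "The app will be readily used and acceptable to CNAs". The sample is set in II.B: "Feasibility will be tested with five CNA volunteers (n=5) who will each record a 2-hour care session".

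Two sections give a numeric criterion for the usability scale:

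- II.C, Aim 1: "10-item usability scale (The System Usability Scale) with an acceptability benchmark of 50% or higher".
- V.A.1, Aim 1, where the analysis is a 10-item usability scale: "Success will be determined by a cumulative score of 80% or more".

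II.C also contains an 80% figure, but for something else, the app's detection of diminutives: "diminutive accuracy testing benchmark of 80% or higher".

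The instrument is described in II.B under Aim 3 as the "System Usability Scale (SUS), a validated 10-item industry standard survey to rate" four aspects of app use. Response options, scoring range and neutral point are not given there or elsewhere. The only other evidence on acceptability in Aim 1 is qualitative and has no pass mark: "The CNAs will be interviewed about use of the app, providing additional data to improve the system for Aim 2 testing".

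**The concern.** The first problem is a contradiction. The same five forms could be reported as meeting the acceptability benchmark under II.C and as not successful under V.A.1. Nothing in the documents says which section governs.

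The second problem is how the contradiction might be resolved. A request merely to reconcile the two figures could be met by keeping 50%. If that mark lies at or below the point where raters have no view, a pass says little about whether CNAs find the app acceptable, which is what Aim 1 is meant to demonstrate. At stake is whether the Aim 1 report can support its acceptability claim.

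**Working it through.** The plan states no error rate, pass probability or interval for either mark, so it has no figure of its own to reproduce. The check asks how often each mark is met by five CNAs who are indifferent, and then by five who mildly dislike or clearly like the app.

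**Inputs from the documents:** n = 5 CNAs (II.B); 10 items (II.B, II.C, V.A.1); marks of 50% (II.C) and 80% (V.A.1).

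**Assumptions, because the scoring is not given:** five response options per item, coded 0 to 4 or 1 to 5, symmetric about the middle; between-CNA SD of 12.5 to 20 points where a normal model is used; independent CNAs.

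**1. The 50% mark under indifference, three readings**

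- *Mean score on a 0 to 100 scale.* Item sum (0 to 40) × 2.5. All-neutral answers give 10 × 2 × 2.5 = 50, which passes with certainty. With independent random answers, the exact distribution of the 50 item responses (total 0 to 200, pass at 100 or more) gives P(pass) = 0.520 for uniform answers. Four symmetric response shapes give 0.516 to 0.532.
- *Share of CNAs favourable.* At least 50% of five means at least 3. With p = 0.5, P(X ≥ 3) = (10 + 5 + 1)/32 = 0.500. With a true share of only 40%, P(X ≥ 3) = 0.317. An observed 3 of 5 has an exact 95% interval of 15% to 95%.
- *Raw sum as a percentage of the maximum.* Items 1 to 5, maximum 50. All-neutral answers give 30/50 = 60%, which passes. Uniform random answers give P(pass) = 0.995, and the four shapes give 0.98 or more.

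Across the readings the range is 0.50 to 1.00.

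**2. The 50% mark away from indifference (0 to 100 score, normal model)**

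P(mean ≥ 50) = 1 − Φ((50 − μ)/(SD/√5)), where SD/√5 = 5.59 for SD 12.5 and 8.94 for SD 20.

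| True mean μ | SD 12.5 | SD 20 |
|---|---|---|
| 40 | 0.04 | 0.13 |
| 45 | 0.19 | 0.29 |
| 50 | 0.50 | 0.50 |
| 60 | 0.96 | 0.87 |

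So the mark usually rejects a clearly disliked app. It does not separate neutral from favourable.

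**3. The 80% mark (mean score)**

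At μ = 50: P = 1 − Φ(30/(SD/√5)), which is below 0.001 for SD 12.5 to 20 and at most 0.004 even for SD 25. At μ = 70: P = 1 − Φ(10/5.59) = 0.04 and 1 − Φ(10/8.94) = 0.13. It discriminates well against indifference but is strict for a favourably rated app.

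**4. An alternative: at least 4 of 5 CNAs strictly above neutral**

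- Indifference: at most p = 0.5 per CNA, so P(X ≥ 4) = (5 + 1)/32 = 0.1875. It is lower if exactly neutral scores can occur, because these do not count.
- μ = 70: p = Φ(20/12.5) = 0.945, or Φ(20/20) = 0.841. Then 5p⁴(1 − p) + p⁵ = 0.97, or 0.82.

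**The case against.** The strongest case against is that the plan already contains a rule that discriminates. Under the 80% score in V.A.1, indifferent CNAs almost never pass, so weakness at the 50% mark matters only if the conflict is settled at 50%. That is correct, and it is why the contradiction comes first here. The second part still adds something, because reconciling at 50% would leave the plan consistent and uninformative.

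A reader might infer two stronger things from the II.C wording. One is that 50% *is* the scale's indifference point. The documents do not support this as fact. They give no scoring; on the raw-sum reading neutral is 60%, and on the share reading 50% is a proportion of people and not a point on the scale. The other is that the 50% rule shows nothing at all. It does screen out a disliked app, as the figures at a true mean of 40 show.

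It can also be said that Aim 1 is a five-volunteer step meant to find needed modifications, that CNAs are interviewed whatever the score, that no go/no-go decision is tied to the score, and that acceptability is assessed again with the same scale in Aim 3. All of this stands and limits the consequences. It does not remove the contradiction, since the protocol chose to state a pass mark and states two.

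**Conclusion.** The point holds, and it is minor. II.C and V.A.1 give incompatible pass marks, 50% and 80%, for what both describe as the 10-item usability scale in Aim 1. This rests on the text alone.

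That 50% should not be the surviving mark rests on assumed scoring, but not on any single assumption: every reading tried gives indifferent CNAs a pass probability of at least one half. The figures at true means other than neutral also depend on the 0 to 100 scale and on the assumed SD of 12.5 to 20.

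The effect is confined to the Aim 1 acceptability conclusion. The Aim 2 group comparison does not use this score.

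**What to change.** Delete the 50% benchmark in II.C and state one identical criterion in II.C and V.A.1. With it, state how the 10 items are scored, what value is neutral, and whether the criterion applies to the mean score or to the share of CNAs. The default is the 80% score already in V.A.1. Report a result between neutral and the threshold as *not shown acceptable; modify before Aim 2*, which fits the purpose II.B gives for this step.

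The cost is protocol wording, with no added participants or data. The downside should be stated openly: with five raters, an app with a true mean of 70 would reach an 80% mean score only about 4% to 13% of the time. If the sponsor finds that too strict, a rule of at least 4 of 5 CNAs strictly above neutral passes at most about 19% of the time under indifference and about 82% to 97% at a true mean of 70. The two rules are not interchangeable. They could give opposite answers for a favourably rated app, so the choice should be made and written down before the Aim 1 data are collected.

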Audio recording supports precise measurement of verbal communication including duration, intensity, and patterns and is less invasive than videotaping, encouraging natural communication and maintaining privacy. Recordings can be reviewed repeatedly to verify accuracy and reliability. Limitations are (1) alteration of natural speech and behavior due to the awareness of recording and (2) inability to control for environmental factors such as noise. Research has established that NH staff do not significantly modify communication if recording is presented in a nonjudgmental manner^{60,61} and this was confirmed in the PI's

research.⁴³ The audio recording protocol is designed to measure communication in NHs⁶² and health care settings;⁶³ it was effective in the PIs research, uses measures to limit the Hawthorne effect (i.e., minimally obtrusive recording equipment), and will record each CNA during the same time periods from day to day to assure consistency.^{8,27,42-44,64,65}

Preliminary Effects Testing (Aims 2): We will test preliminary effects of app feedback on elderspeak use in audio-recorded staff communication. A cluster randomized trial will be conducted in six NHs that participate in CHATO training. We will compare the immediate and delayed-feedback control groups on elderspeak (diminutive) changes after participation in CHATO. We hypothesize that staff who receive immediate feedback will demonstrate greater reductions in use of diminutives, the most common and recognizable marker of elderspeak, compared to control group staff before they receive delayed feedback. We will validate app accuracy by comparing app results to psycholinguistic coding using our established protocols for data reduction, transcription, and coding.^{8,44,66}

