Six NHs will participate in audio recording of CNA communication before and after CHATO (see letters of support). These NHs will be randomly assigned to immediate feedback (n=3; recording with app feedback on elderspeak use) or control (n=3; recording with end of study feedback) groups. In each NH, 12 CNAs will be recruited using strategies successful in our past research such as announcing the research opportunity at staff meetings. Enrollment of 12 CNAs per NH allows for levels of attrition experienced in our prior studies. If fewer than 30 CNAs per group complete recordings, more NHs will be added. CNA volunteers (at least 30 per group) will record their communication in 2-hour care sessions on 1 day before and on 3 days after completing CHATO.

In both NH groups, 12 CNAs will be recorded for a 2-hour shift prior to participating in CHATO training (baseline). The URL link to complete the CHATO modules will be provided for the CNAs as well as other NH staff. Staff will be expected to complete the training over a 2-week period. After completion, the 12 CNAs from each NH who are participating in the app testing will be recorded again within a week of completing training (post-CHATO time 1), then approximately 1 week later (post-CHATO time 2), and finally another week later (post-CHATO time 3). Immediate feedback NH CNAs will receive the app feedback at the end of each post- CHATO recording session, while control group NH CNAs will not receive app feedback until the end of their post-CHATO time 3 recording sessions.

Each NH will provide a letter of interest, acknowledging random assignment, committing to engage staff in CHATO training, and agreeing to provide descriptive and cost data including number and types of staff and average wages. Each NH will be approved prior to participation by the KUMC IRB. NH size and census, profit status, proportion of residents with dementia, presence of a special care unit, staffing and turnover ratios, Medicare star rating, antipsychotic prescription rate, and Medicaid case mix will be collected from Nursing Home Compare and NH reports. Medicaid case mix is a measure of resident acuity or care needs that is used to determine Medicaid reimbursement rates and has been used in research to control differences in care needs across NHs.^{67,68} Participating NHs will be encouraged to engage all direct care staff, including housekeeping, dietary, and administrative staff in the training.

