CHATO is presented in three modules.^{10,70} Session 1 introduces effective versus ineffective communication. Participants identify communication issues in video vignettes. Session 2 focuses on identification and negative effects of elderspeak, using video-recorded examples. Session 3 includes strategies for improved communication based on assessment of each resident's abilities. Participants critique communication in videos and correct transcripts to eliminate elderspeak. Training is limited to three 1-hour sessions to assure feasibility in busy NHs. The modules include moderated discussion and interactive exercises that must be completed to advance through the program. This assures content fidelity and dose of the intervention. CHATO is provided to as many staff as possible to achieve facility-wide effects of reduced elderspeak.⁷⁴ The modules contain pre- and post-tests (scenario-based questions and rating of staff communication in video clips) to evaluate knowledge gain. The Modified Duke Diffusion of Innovation⁷⁵ survey provides information about CHATO participant intentions to use learned skills in practice and the likelihood for translation.

Audio Recordings. CNAs will be recorded for 2 hours on 1 day in the week before and 3 days in the 2 weeks after CHATO training. To ensure consistency, every attempt will be made to make post-CHATO recordings at the same time of day. CNAs will be permitted to turn the recording unit off when they do not wish to be recorded. Although this may limit validity of the recordings, it assures privacy and participation. Recordings will be time coded and take place during morning care when elderspeak and BPSD are most frequent.^{44,76,77} To minimize attrition, CNAs will be recruited just prior to their NH's participation in CHATO training. *A priori* randomized order for NH participation will control for historical effects. Intention-to-treat analyses will be used. The feedback group CNAs will receive automated feedback on elderspeak use after each post-CHATO recording session. The control group will receive feedback for all recording sessions after their final (third post-CHATO recording session). The Project Director will download recordings for both groups and delete them from the iPod Touch.

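### The Aim 2 model uses the single pre-CHATO recording both as baseline covariate and as a session level of the outcome, so the group-by-session test is an unadjusted change score and the residual variance matches no defined analysis

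*Combined protocol and SAP*

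**What the plan says.** The Aim 2 model is set out in section II.C. Its fixed effects are "Baseline diminutive use, group (feedback vs. no feedback), recording session (pre- and post CHAT sessions 1, 2, and 3", followed by the interaction of group with session. Nursing home (NH) is the only random effect named. For the repeated recordings, "an appropriate covariance pattern will be determined from data". The model may be linear or generalized linear, according to how the outcome is distributed.

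Section II.B shows that baseline and the pre-CHATO session are the same measurement: "12 CNAs will be recorded for a 2-hour shift prior to participating in CHATO training (baseline". The Audio Recordings paragraph confirms a single pre-training day: "CNAs will be recorded for 2 hours on 1 day in the week before and 3 days in the 2 weeks after CHATO training".

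The comparison of interest is between the "immediate and delayed-feedback control groups on elderspeak (diminutive) changes after participation in CHATO". Feedback-arm CNAs "will receive the app feedback at the end of each post- CHATO recording session". Section II.C adds a second purpose: "Aim 2 will estimate variability, effect sizes, and intracluster correlation for a future larger-scale study". Section V.A repeats only the model family and does not settle how the pre-CHATO recording is used.

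**The concern.** A baseline value can be a covariate for later outcomes, or it can be the first of the repeated outcomes. The plan makes it both, so the pre-CHATO rows are regressed on themselves.

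Three things follow in a linear mixed model.

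- The hypothesis concerns change, so the natural test is group by session against the pre-CHATO level. The baseline covariate does nothing for that test, although a reader of II.C would think the test is adjusted.
- Under patterns with one common variance, the pre-CHATO rows are partly explained by themselves and pull the residual variance down.
- If the pattern chosen from the data gives the pre-CHATO session its own variance, the fit degenerates.

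At stake are the precision of the main comparison in a small trial and the meaning of the variance estimates promised for the next one.

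**Working it through.** **Inputs.** From II.C: 30 CNAs per group, 10 per NH on average, ICC 0.001 to 0.01, cluster-size coefficient of variation 0.25, two-sided 0.05, degrees of freedom from subjects. The plan gives no within-CNA correlation r for diminutives, so I assume 0.3, 0.5 and 0.7.

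I.B offers a rough proxy from the earlier CHAT trial (total elderspeak): baseline SD 18.7, change SDs 20.0 and 22.0. If pre and post SDs are equal, r = 1 − 20.0²/(2 × 18.7²) = 0.43 and 1 − 22.0²/(2 × 18.7²) = 0.31.

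**The plan's own figure.** The design effect is 1 + ((1 + 0.25²) × 10 − 1) × ICC, which is 1.010 at ICC 0.001 and 1.096 at 0.01. A t-test with 58 df then detects 0.739 and 0.770 SD at 80% power (0.757 at ICC 0.01 with a normal approximation). The stated 0.74 to 0.76 SD reproduces. It is a plain comparison of group means, so the double use of baseline does not alter it.

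**Step 1: cancellation.** The covariate term b·x is constant within a CNA, so it drops out of any post-minus-pre contrast. In simulated complete data with six NHs of unequal size, the fitted session 3 interaction equalled the raw difference in mean change to six decimals under independence, compound symmetry and AR(1): −1.038724 at r = 0.35 and −0.927264 at r = 0.5. Under compound symmetry the SE was also the same with and without the covariate (0.283 and 0.248). A post-only baseline-adjusted fit gave different results: −0.864 (SE 0.235) and −0.880 (SE 0.228).

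**Step 2: precision lost.** Take single-recording variance 1, equal correlation r and no NH effect. Per-CNA variances are:

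- one session: change 2(1−r), adjusted 1−r²; SE ratio √(2/(1+r));
- mean of sessions 2 and 3: change 3(1−r)/2, adjusted (1−r)(1+2r)/2; SE ratio √(3/(1+2r)).

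Power at 0.74 SD is Φ(0.74/√(2v/30) − 1.96), where v is the per-CNA variance. For r = 0.3 and one session, v = 1.40 gives Φ(2.42 − 1.96) = 68%, and v = 0.91 gives Φ(3.00 − 1.96) = 85%.

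| r | SE ratio, one session | Power, change v adjusted | SE ratio, sessions 2–3 | Power, change v adjusted |
|---|---|---|---|---|
| 0.3 | 1.24 | 68% v 85% | 1.37 | 80% v 97% |
| 0.5 | 1.15 | 82% v 91% | 1.22 | 91% v 98% |
| 0.7 | 1.08 | 96% v 98% | 1.12 | 99% v 99.8% |

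At the proxy values the one-session figures are 68% v 85% (r = 0.31) and 77% v 89% (r = 0.43).

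**Step 3: residual variance under compound symmetry.** The pre-CHATO rows have slope 1 on themselves and each post session has slope r, so the pooled slope is b = (1+3r)/4. Averaging the residual variances (1−b)² for pre and 1−r²+(b−r)² for each post session gives (3/16)(5+3r)(1−r).

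| r | As written | Post-only adjusted, 1−r² | Unadjusted | As written / adjusted |
|---|---|---|---|---|
| 0.3 | 0.77 | 0.91 | 1 | 0.85 |
| 0.5 | 0.61 | 0.75 | 1 | 0.81 |
| 0.7 | 0.40 | 0.51 | 1 | 0.78 |

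This is the total CNA-level variance on the diagonal of the covariance pattern. Large-sample fits with compound symmetry or AR(1), as truth and as fitted pattern, put it 11% to 23% below the adjusted value.

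Model SEs for a group difference at one post session are then about 9% to 12% too small. Simulated type I error was about 7% to 8% at nominal 5% (compound symmetry, no NH effect, subject-level critical value).

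**Step 4: separate variance for the pre-CHATO session.** The pre residual is proportional to 1−b, so with 60 CNAs the profile log-likelihood contains −60 ln(1−b). It rises by 60 × ln 10 = 138 for each tenfold approach of b to 1, without limit. At that limit the post-session variance is 2(1−r) = 1.40, 1.00 and 0.60, above the adjusted values. The direction of the distortion therefore depends on a pattern that the plan leaves open.

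**The case against.** The strongest reply is that no invalid inference is shown. The interaction test is a correct change-score test, the stated detectable difference stands, and this is a preliminary-effects study. That is true. What remains is lost precision and a variance estimate without a clear meaning. Any type I inflation depends on a contrast and degrees of freedom that the plan does not fix.

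A kinder reading takes pre and post as a description of the recording schedule. But the parenthesis defines the levels of the fitted session factor, so a plan that relies on this reading still needs the sentence changed.

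Several limits do stand:

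- Coding output "will be used to tabulate frequencies for each code", so a count model is plausible. The exact cancellation does not carry over to a nonlinear link, and I have not quantified that case.
- With missing sessions the identity is only approximate. With about 17% of post sessions missing, one example gave −1.196 against a raw −1.243.
- Under compound symmetry the within-CNA variance component is 1−r in every version. Only the total variance shifts.
- Harm to the ICC is not shown. At a true 0.01 with six NHs, the mean estimate was 0.011 to 0.013 as written, 0.017 to 0.018 post-only and 0.020 to 0.027 unadjusted, with 49% to 59% of estimates at zero. That is mostly noise.
- An analyst would probably notice the degenerate fit in step 4 as non-convergence.
- r = 0.7 has no support in the documents. The proxy values lie at the low end, where the loss is larger.

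**Conclusion.** The concern holds and should be fixed. As written, the Aim 2 model uses one measurement as predictor and response. For a Gaussian model with complete data, the group-by-session test against the pre-CHATO level gains nothing from the listed covariate. Its SE for one session is 8% to 24% larger than with proper adjustment for r between 0.7 and 0.3. Near the proxy correlations, one-session power at 0.74 SD falls by about 12 to 17 percentage points. Below r = 0.5 the change-score variance 2(1−r) exceeds 1, so that test is less sensitive than the plan's own unadjusted calculation.

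Under compound symmetry the total residual variance is 15% to 22% below that of a baseline-adjusted analysis. A future trial sized on it but analysed with baseline adjustment would be too small by the same proportion, if the planning variance is read from this model.

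These figures assume 30 CNAs per group, equal variances and correlations across sessions, no NH effect and a normal approximation. Power for sessions 2 and 3 also assumes the same effect at both.

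**What to change.** In II.C, use the pre-CHATO recording once.

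- **Option A (simpler):** model post-CHATO sessions 1 to 3 as outcomes, with the pre-CHATO value as covariate, group, session, group by session, an NH random effect and a CNA-level covariance.
- **Option B:** keep all four sessions as outcomes, drop the covariate and constrain the arms to a common pre-CHATO mean. This assumes the arms are comparable at baseline. With six NHs, and CNAs recruited just before their NH takes part, that needs justifying.

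Name the primary contrast. Because feedback comes at the end of each post-CHATO recording, time 1 is recorded before any feedback, so the plan should say whether time 1 enters the contrast.

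State whether the variance and ICC reported for the future trial are baseline-adjusted (A) or unadjusted (B). The two differ and must match the analysis that trial will use. If a count model is chosen, the same single use of the pre-CHATO recording should apply.

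The cost is two or three sentences in II.C and no new data.
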